## **Budget**

This study will utilize all the routine radiological and biochemical tests that are part of the medical care of these patients. There will be no specific blood or radiological testing that will be performed or ordered only for the purpose of the study. TACE is considered a standard of care for HCC patients and all insurance companies including MediCal and Medicare pay for this treatment. Many insurers will cover proton treatment for HCC. This study does not incur any extra expenses that require additional funding.

## **Appendix 1**

## **Tumor Classification**

### **Milan Criteria**

Solitary lesion  $\leq$  5 cm or  $\leq$  3 lesions, none of  $>$  3 cm

### **San Francisco Criteria**

Solitary lesion  $\leq$  6.5 cm or  $\leq$  3 lesions none  $>$  4.5 cm and total tumor diameter  $\leq$  8 cm

## Appendix 2

### Child-Pugh-Turcotte Score and Class

#### **1. Bilirubin (mg/dl)**

- <2 OR < 4 for patients with primary biliary cirrhosis (1 point)
- 2-3 OR 4-10 for patients with primary biliary cirrhosis (2 points)
- >3 OR > 10 for patients with primary biliary cirrhosis (3 points)

#### **2. Albumin (g/dl)**

- >3.5 (1 point)
- 3.5-2.8 (2 points)
- <2.8 (3 points)

#### **3. PT prolongation (INR)**

- <4 seconds (<1.7) (1 point)
- 4-6 seconds (1.7-2.3) (2 points)
- >6 seconds (>2.3) (3 points)

#### **4. Ascites**

- Absent (1 point)
- Slight (2 points)
- Moderate (3 points)

#### **5. Encephalopathy**

- Absent (1 point)
- Mild (I-II) (2 points)
- Severe (III-IV) (3 points)

Class Interpretation:

**Class A: 5-6**

**Class B: 7-9**

**Class C: 10-15**

### **Stages of Hepatic Encephalopathy**

Stage 1: Euphoria or depression, mild confusion, slurred speech, disordered sleep

Stage 2: Lethargy, moderate confusion

Stage 3: Marked confusion, incoherent speech, sleeping but arousable

Stage 4: Coma, initially responsive to noxious stimuli, but later unresponsive

## Appendix 3

### **Transarterial Chemoembolization Treatment Protocol**

This procedure is done with the help of fluoroscopy (type of x-ray) imaging. A catheter (long, narrow tube) is inserted into the femoral artery in the groin and is threaded into the aorta (the main artery of the body). From the aorta, the catheter is advanced into the hepatic artery. Once the branches of the hepatic artery that feed the liver cancer are identified, the chemotherapy is infused and the arterial branch that supply the tumor is embolized using Gel Foam or Lipoid. The whole procedure takes one to two hours, and then the catheter is removed.

The patient generally stays in the hospital overnight for observation. A sandbag is placed over the groin to compress the area where the catheter was inserted into the femoral artery. The nurses periodically check for signs of bleeding from the femoral artery puncture. They also check for the pulse in the foot on the side of the catheter insertion to be sure that the femoral artery is not blocked as a result of the procedure. (Blockage would be signaled by the absence of a pulse).

Generally, the liver tests increase (get worse) during the two to three days after the procedure. This worsening of the liver tests is actually due to death of the tumor (and some non-tumor) cells. The patient may experience some post-procedure abdominal pain and low-grade fever. However, severe abdominal pain and vomiting suggest that a more serious complication has developed. Imaging studies of the liver are repeated in six to 12 weeks to assess the size of the tumor in response to the treatment.

## **Appendix 4**

### **Proton Beam Radiotherapy Treatment Protocol**

Procedures for HCC subjects randomized to proton therapy:

Immobilization and Treatment planning CT Scan

Immobilization

All patients will be fit with a full-body immobilization device to limit day-to-day set up variations and to reduce interfraction alignment errors. This will be accomplished by placing the subject supine within a half cylinder PVC shell then adding two-part foam to create a rigid mold. This device will be used for all subsequent patient treatments to provide reproducible patient alignment.

Treatment Planning CT

Subjects will undergo CT simulation in the department of radiation medicine while lying in their immobilization device. All images will be acquired with IV contrast enhancement during the arterial phase. Image acquisition will take place only when the subject is actively breath holding at end-expiration. Imaging will cover the entire abdomen from above the right hemi-diaphragm through the 5th lumbar vertebral body. Recommended scan spacing is 3x2 mm.

Target Volume and Normal Tissue Definition

Gross Tumor Volume (GTV) – The GTV will be contoured on each CT image and will include all areas of known disease as identified on the planning images and/or seen on diagnostic CT or MRI.

Clinical Target Volume (CTV) – A CTV will be created to extend 1cm beyond the GTV in all dimensions. This volume may be edited if it extends beyond the liver parenchyma. The CTV will be edited so that it will not include organs known not to be involved by the tumor (i.e. abdominal wall, kidney, bowel).

Normal Tissue Definition – All organs and normal tissue regions not targeted for treatment will be contoured for dose-volume-histogram calculations. The entire liver will be contoured in all cases taking care to omit the gallbladder and portal vessels. Bowel that lies near the target volume and the right kidney should also be routinely contoured.

3-Dimensional Treatment Planning, Dose Definitions, and Normal Tissue Constraints

Treatment Planning

A computerized 3-Dimensional treatment plan will be generated utilizing the Odyssey treatment planning system at LLUMC. The target region will be the CTV with the additional margin to account for daily setup variations and energy specific beam penumbra. Beam angles typically used include right lateral, posterior, and posterior oblique beams.

Anterior beams should be used only in selected patients, as these beams will not be within the immobilization device. Beam weighting and custom editing of beams shaping devices may be utilized to optimize the final dose distribution. All computer simulated treatment plans require approval by the treating physician prior to patient treatment.

#### Proton Dose to CTV

All doses will be prescribed to a point at or near the center of the CTV target region. The total dose delivered will be 70.2 CGE given in 15 fractions over a three-week course. The uniformity of dose across the target region will not vary by more than 10% of the prescribed dose. At least two beams will be treated each day to reduce the dose at the beam entry site.

#### Normal Tissue Constraints

**Liver** – Dose constraints for the liver will be based on dose-volume histogram (DVH) analysis from the Odessey treatment planning system. The dose that falls within the GTV will be excluded from the DVH calculation; however dose given to liver tissues outside the GTV but within the CTV will be included. The treatment-planning goal will be to limit the volume of liver receiving more than 30 Gy to 33% or less. If this constraint cannot be met, the additional CTV margin may be changed from 1cm to 5mm. This will be considered a minor protocol violation and will be noted in the patient record for future analysis.

**Bowel** – If any portion of the bowel falls within the 90% isodose volume field reductions will be required. Full margins will be used for the first seven fractions of treatment. The following 8 fractions will be delivered with modifications that limit dose to the bowel surface to 50% of the remaining dose. In these cases the minimum dose to the CTV and GTV will be recorded for future analysis.

**Kidney** – At least 50% of the right kidney will receive no more than 20 Gy. This constraint assumes complete sparing of the left kidney.

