## **Proton Beam Radiotherapy**

Proton beam radiotherapy has physical properties that target the actual tumor mass and spare large portions of nearby normal tissues. Phase I and II trials demonstrated the safety of this treatment modality in decompensated patients with cirrhosis with HCC. Few trials in Southeast Asia and the United States demonstrated that proton beam could be an effective treatment that may improve survival and control tumor progression. Tokuyue et al. treated 79 patients who had HCC with proton beam radiotherapy (12). A median total dose of 72 Cobalt gray equivalents in 16 fractions was delivered. At 5 years, local tumor control and survival rates were 89% and 27% respectively. Kawashima et al. used the same fractionation scheme in 30 patients with HCC with an indocyanine green retention rate at 15 minutes. Complete disappearance of tumors occurred in 24 patients (80%). The 2-year local regression-free rate in that study was 96%, and the 1-year and 3-year survival rates were 77% and 62% respectively (13). Eight patients developed hepatic insufficiency, which presented as ascites, elevated transaminase levels, and/or asterixis from 1 to 4 months after therapy (13). Bush et al., in a phase II trial where 34 patients with HCC completed 15 sessions of total 63 cobalt Gray equivalents, 75% local tumor control rate and overall survival rate of 55%. Six patients underwent liver transplantation 6 to 18 months after proton therapy. In 2 patients, there was no evidence of tumor pathology, demonstrating that proton therapy can eradicate HCC (14). A complete pathologic response was also observed by Merle et al (15). Risks involved in proton treatment include internal bleeding, radiation hepatitis (elevation in liver enzymes), worsening liver function (elevation in

bilirubin and INR) and perforation of the surrounding solid organ such as small bowel and stomach.

Proton beam radiotherapy has been associated with some of the best outcomes in HCC patients; however, further studies are needed to compare proton to other treatments.

In this randomized trial we wish to compare head-to-head the efficacy of proton beam radiotherapy versus TACE in treating patients with unresectable HCC.

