## **Patients**

Patients with cirrhosis and HCC who are not candidates for surgical resection will be targeted for enrollment. Patients will be recruited from the liver clinics at the Transplantation Institute and Faculty Medical Office. Patients from the Inland Empire area will be invited to participate as well. Community physicians will be informed of the study via mail and will be encouraged to refer their patients for participation (see attached letter No 1). Patients who are qualified to receive both TACE and proton treatments will be included. CT scan of the chest and bone scan within 6 months is required to exclude the presence of metastasis. Macrovascular invasion will be excluded using MRI or CT scan of the abdomen that will be performed within 3 months of enrollment.

Interventional radiologists and a radiation oncologist at LLUMC will evaluate the patient's case independently prior to randomization if the candidate is qualified to receive both treatments. Contraindications to receive TACE are: Child class C, hypovascular lesion and active sepsis. Contraindications to proton are: tense ascites requiring frequent paracentesis or proximity to a hollow organ such as the stomach or small intestine.

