## ***Exclusion Criteria***

1. Patients who are candidates for surgical resection
2. Patients with lesion < 2 cm
3. Patients who have contraindication to receive either TACE or proton
4. Patients with serum alpha fetoprotein > 500
5. Patients with metastasis or macrovascular invasion
6. Patients treated previously for HCC by any locoregional treatment
7. Patients with prior liver transplant
8. Patients with Child class C
9. Patients with MELD score of > 25 (Appendix 5)
10. Patients with other comorbid diseases that may impact survival
11. Patients with ongoing alcohol intake
12. Patients with active sepsis
13. Patients with gastrointestinal bleeding within a week
14. Patients unwilling to sign informed consent form
15. Patients with history of noncompliance

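### The bowel dose rule has a step that runs the wrong way: bowel just outside its 90% trigger could receive about 8 to 15 CGE more than bowel inside it, and the rule does not fit the eligibility text

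*Combined protocol and SAP*

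**What the plan says.** Appendix 4, Proton Dose to CTV, sets the course: "The total dose delivered will be 70.2 CGE given in 15 fractions over a three-week course". It adds a uniformity allowance: "The uniformity of dose across the target region will not vary by more than 10% of the prescribed dose".

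Appendix 4, Normal Tissue Constraints, gives bowel one conditional rule. The trigger is "If any portion of the bowel falls within the 90% isodose volume field reductions will be required". The consequence comes in two stages: "Full margins will be used for the first seven fractions of treatment", and then "The following 8 fractions will be delivered with modifications that limit dose to the bowel surface to 50% of the remaining dose". No cumulative bowel dose is stated, and nothing is said about bowel outside the 90% isodose. Liver and kidney, by contrast, have dose-volume goals that apply to every plan. The stomach is not mentioned in that section.

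Three other places bear on this:
- The Proton Beam Radiotherapy section lists among the risks "perforation of the surrounding solid organ such as small bowel and stomach".
- The Patients section makes "proximity to a hollow organ such as the stomach or small intestine" a contraindication to proton, with no distance or dose attached. Exclusion criterion 3 then removes "Patients who have contraindication to receive either TACE or proton".
- Appendix 4, Target Volume and Normal Tissue Definition, asks for routine contouring of bowel near the target, so it expects such patients to be treated.

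**The concern.** A rule that protects an organ near the target would be expected to give a total dose that does not rise as the organ moves out to a lower isodose. This rule acts only inside the 90% line, and there it cuts the last eight fractions sharply. A patient whose bowel lies a little further out gets no reduction. Followed to the letter, the rule can leave the second patient's bowel with the higher total.

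Perforation is a risk that the protocol itself attaches to proton treatment, and the gap exists in one arm of a trial whose primary endpoint is overall survival. There is also a question of who is in the trial. Patients near a hollow organ are excluded in one place and planned for in another, so two radiation oncologists could screen and plan the same patient differently.

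**Working it through.** The plan states no cumulative bowel dose, so there is no figure of its own to reproduce. The fraction counts do agree: 7 + 8 = 15.

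**Inputs.** From Proton Dose to CTV: 70.2 CGE, 15 fractions, 10% uniformity allowance. From Normal Tissue Constraints: 90% trigger, 7 full-margin fractions, then 8 fractions with bowel limited to 50% of the remaining dose.

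**Assumptions.** Fractions are equal; the 90% is relative to the prescribed dose; the remaining dose is the prescription of the last 8 fractions.

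**Building blocks.**
- Per fraction: 70.2 / 15 = 4.68 CGE
- First 7 fractions: 7 × 4.68 = 32.76 CGE
- Last 8 fractions: 8 × 4.68 = 37.44 CGE
- Bowel limit over the last 8: 0.5 × 37.44 = 18.72 CGE

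**Bowel inside the trigger.** With r the relative isodose at the bowel, the total is at most r × 32.76 + 18.72.
- r = 0.90: 29.48 + 18.72 = 48.20 CGE (68.7% of 70.2)
- r = 1.00: 32.76 + 18.72 = 51.48 CGE (73.3%)
- r = 1.10, the upper edge of the uniformity allowance: 36.04 + 18.72 = 54.76 CGE (78.0%)

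**Bowel outside the trigger.** There is no reduction, so the total is r × 70.2 with r below 0.90.
- r just under 0.90: just under 63.18 CGE
- r = 0.89: 62.48 CGE
- r = 0.80: 56.16 CGE
- r = 0.70: 49.14 CGE

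**Size of the step**, comparing bowel just outside the line with bowel inside it:
- at the 90% line: 63.18 − 48.20 = 14.98 CGE
- at 100%: 63.18 − 51.48 = 11.70 CGE
- at a 110% hot spot: 63.18 − 54.76 = 8.42 CGE

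**Where the excess ends.** The unreduced total falls to 48.20 CGE at 48.20 / 70.2 = 68.7%, and to 51.48 CGE at 51.48 / 70.2 = 73.3%. So the excess is largest at the line and shrinks to nothing at about the 69–73% isodose. Against the hot-spot case it ends sooner, at 78.0%.

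**Eligibility against planning.** If the proximity exclusion removes everyone with bowel inside the 90% isodose, the bowel rule has nobody to act on. If it does not, such patients can be enrolled, and so can those whose bowel lies slightly further out, where nothing is triggered. The text does not say which is meant.

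**The case against.** The strongest reply is that the rule is an action threshold and not a tolerance. Every sentence in it can be followed at once, and no sentence sets a bowel dose that another breaks. This stands. A reader might infer that the rule contradicts itself, or that the plan allows 63 CGE to bowel. The documents support neither: the 48–55 CGE and the 63 CGE are both derived, the second from the absence of a limit.

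Second, such patients do not go unreviewed. Bowel near the target is contoured, beams may be weighted and reshaped, and the treating physician approves every plan. That is true, and practice may well be better than the rule. But none of these steps carries a numeric bowel limit, so the written plan does not close the gap.

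Third, excluding tumours near a hollow organ narrows the affected group, and it deals with the stomach at screening. This stands in part. The amount of narrowing is undefined, and the exclusion does not fit with a rule for bowel inside the 90% isodose.

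Fourth, a reader might infer that extra perforations will distort the survival comparison. The documents give no count of affected patients and no perforation rate, so that effect is possible but not shown.

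**Conclusion.** The point holds as a discontinuity with an inverted result. Under the three assumptions listed with the calculation, the total that the rule leaves open falls by about 8 to 15 CGE when bowel crosses into the trigger. The direction holds even in the least favourable comparison, a 110% hot spot inside the line. The upper figure applies only at the line and should not be read as the excess for every position down to about 69–73%.

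Separately, the proximity exclusion and the bowel rule do not fit together, and the stomach is named as a risk and as a ground for exclusion but has no dose rule. The case for acting is that a written safety rule gives an inconsistent result, not that an effect on the trial's findings has been demonstrated.

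**What to change.** The sponsor's radiation oncologists should make two reconciliations:

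1. Within Appendix 4, Normal Tissue Constraints: reconcile the trigger for field reduction with the dose that the reduction produces, so that the rule is consistent across bowel positions.
2. Between that section and the rest of the protocol: reconcile it with the proximity contraindication in Patients, exclusion criterion 3, the contouring instruction in Appendix 4 and the risks listed under Proton Beam Radiotherapy. It should then be clear which patients are eligible, and what applies to the stomach.

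The values and the form of the rule are theirs to set; none is proposed here. The amendment is short. The real cost is that some plans may change, possibly with some effect on target coverage. The protocol already has the minimum CTV and GTV dose recorded when the bowel rule is triggered.

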#### Treatment Delivery

Patients will be treated at the proton treatment center at LLUMC. For each treatment, the patient will be placed in their custom-made immobilization device. Orthogonal diagnostic x-ray images will be taken of the treatment area and registered with the digitally reconstructed radiographs created from the planning CT scan. All misalignments greater than 1mm from the established treatment isocenter will be corrected. All beam shaping devices will be verified each day both by the therapy personnel and with the record and verify system. The initial treatment setup and subsequent new treatment fields will be verified by a physician prior to that day's treatment. At least two fields will be treated daily. Treatment will only be given during an active breath hold at end-expiration to minimize respiratory motion of the liver. Fifteen fractions over 3 weeks will be delivered. All patients will be

clinically evaluated, weekly, by the treatment radiation oncologist to assess treatment tolerance and to monitor for acute toxicities.

## Appendix 5

### Model For End-Stage Liver Disease (MELD) Score

The MELD score is calculated using the following equation:

$$3.8 \times \log (e) \text{ (bilirubin mg/dL)} + 11.2 \times \log (e) \text{ (INR)} + 9.6 \log (e) \text{ (creatinine mg/dL)}$$

The equation seeks to calculate a patient's likelihood of dying within three months from their liver disease. It is used by UNOS to allocate organ for liver transplant for patient on the list. Scores range from 6-40. A score of six indicates the least ill patient and a score of forty indicates the sickest patient. The priority for organ allocation is given for patients with the highest MELD score.

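### The MELD equation printed in Appendix 5 does not produce the 6 to 40 scale stated beside it, and exclusion 9 relies on that appendix for its limit of 25

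*Combined protocol and SAP*

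**What the plan says.** Appendix 5 introduces its formula with "The MELD score is calculated using the following equation" and prints three terms: 3.8 times the natural log of bilirubin (mg/dL), 11.2 times the natural log of INR, and 9.6 times the natural log of creatinine (mg/dL). Nothing precedes the first term or follows the last. No floor or cap is given for the laboratory values or the result, and no rounding rule. The text below the formula says "Scores range from 6-40. A score of six indicates the least ill patient", and puts the sickest patient at forty.

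The score is used for eligibility. Item 9 of the Exclusion Criteria is "Patients with MELD score of > 25 (Appendix 5", so the appendix is the definition behind that limit. No other section defines MELD or says how it is obtained at screening.

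Other screens overlap with it. Item 8 excludes Child class C. Item 10 excludes "Patients with other comorbid diseases that may impact survival". The Patients section adds "Contraindications to receive TACE are: Child class C, hypovascular lesion and active sepsis", and has interventional radiology and radiation oncology assess each case "independently prior to randomization if the candidate is qualified to receive both treatments".

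**The concern.** An equation described as the way to calculate a score should return values on the scale claimed for it. This one has neither a minimum of 6 nor a maximum of 40. Someone calculating from the appendix and someone working on the stated scale could therefore hold different numbers for the same patient.

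What is at stake is consistent application of exclusion 9. If the two numbers differ near 25, a patient could be eligible on one and excluded on the other. MELD is not an endpoint and has no named role in randomization or analysis, so the consequence stops at who is enrolled.

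**Working it through.** **Inputs.** The coefficients 3.8, 11.2 and 9.6, the natural logs and the 6 to 40 scale are from Appendix 5. The limit of 25 is exclusion 9. Child-Pugh points are from Appendix 2. The laboratory values are illustrative and do not come from the plan. They are given as bilirubin/INR/creatinine.

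**Step 1: try to reproduce the stated scale.** Score = 3.8 ln(bilirubin) + 11.2 ln(INR) + 9.6 ln(creatinine).

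- 1/1/1: 0 + 0 + 0 = 0
- 1.5/1.3/1.0: 1.54 + 2.94 + 0 = 4.5
- 0.6/1.0/0.8: -1.94 + 0 - 2.14 = -4.1
- 30/4/4: 12.92 + 15.53 + 13.31 = 41.8

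The first three fall below 6 and the last exceeds 40, so the scale is not reproduced. Base-10 logs do not help, since 1/1/1 still gives 0.

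**Step 2: could one lost constant explain it?** Call it k. The low example needs k of at least 6 + 4.08 = 10.1. The high example needs k of at most 40 - 41.76 = -1.8. No k satisfies both. The two examples span 41.76 + 4.08 = 45.8 points, against a scale 40 - 6 = 34 points wide. With k = 6 they become 1.9 and 47.8. Bounds of some kind are needed whether or not a constant is also missing.

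**Step 3: what happens at the limit of 25?**

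- Truncation only: values below 6 become 6 and values above 40 become 40. The limit lies inside the range, so nobody moves across it.
- Missing constant k: a patient passes on the printed score but exceeds 25 on the stated scale when 25 - k < printed score ≤ 25. The documents give no k. Assuming 6, so that the stated minimum occurs when all three values equal 1, the band is above 19 and up to 25. For k = 4 it starts at 21, and for k = 8 at 17.

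**Step 4: can patients in that band be Child class A or B?** Assume albumin above 3.5, no ascites, no encephalopathy (1 point each) and no primary biliary cirrhosis.

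- 1.9/2.2/2.3: 2.44 + 8.83 + 8.00 = 19.3, or 25.3 with k = 6. Child: bilirubin 1 + INR 2 + 3 = 6, class A.
- 4/2/2: 5.27 + 7.76 + 6.65 = 19.7, or 25.7 with k = 6. Child: 3 + 2 + 3 = 8, class B.
- 4/3.5/1.0: 5.27 + 14.03 + 0 = 19.3, or 25.3 with k = 6. Child: 3 + 3 + 3 = 9, class B.

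These cross 25 only if k exceeds about 5.7, 5.3 and 5.7 respectively (25 minus the unrounded printed score). At k = 4 none of the three would. The third example shows that the band does not require raised creatinine.

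**The case against.** The strongest reply is that the sentence giving the range is itself the bound: results below 6 are reported as 6, and results above 40 as 40. The wording about the least ill and sickest patients fits that reading, and exclusion 9 would then be untouched. The reading is possible, but the appendix does not say so. It presents the equation as the calculation and never says how the equation and the range are joined. The objection does establish that showing bounds are needed does not show that a constant is missing.

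A trailing constant could also have been lost when the PDF was read. Nothing in the text marks a gap, and by Step 2 a restored constant alone would still not give 6 to 40.

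The documents do not say whether staff calculate by hand or use some other tool. If they use another tool, no patient need be misclassified, but the appendix may then not describe the score applied.

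A reader might infer that the plan will enroll patients who should be excluded. The documents do not support that: it needs both a missing constant, which they never mention, and calculation from the printed equation. A reader might equally infer that the band is narrow or the number affected small. That is not supported either. The third example in Step 4 reaches the band with creatinine 1.0, and the documents give no distribution of laboratory values. The other screens do limit exposure, but none of them defines MELD.

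**Conclusion.** The mismatch holds on the text: as printed, the equation does not yield the scale stated with it, and an eligibility criterion depends on that appendix. Confidence is high for this part only.

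The effect on eligibility is conditional. Under truncation it is nil. Under a missing constant (assumed 6, range 4 to 8) it covers printed scores above 19 (21 to 17) and up to 25, in patients who can be Child class A or B, and only if staff use the printed equation. How many patients that would be is unknown. Sample size and the primary analysis do not change. Severity is minor.

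**What to change.** Reconcile the Appendix 5 equation with the scale given there: write out any constant, the bounds (saying whether they apply to the score or to the laboratory values) and the rounding. State in exclusion 9 that the limit applies to that reconciled score. Check any screening worksheet against it. No view is taken here on what the cut-off should be.

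The cost is a short correction to one appendix, a clause in one criterion and a worksheet check. The downside is that some borderline patients may change eligibility.
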